8 MONITORING

Routine monitoring of study sites is described in Section 11.2.

Clinical site monitoring is conducted to ensure that the rights and well-being of human subjects are protected, that the reported study data are accurate, complete, and verifiable, and that the conduct of the study is in compliance with the currently approved protocol and amendment(s) as applicable, with GCP, and with applicable regulatory requirements. Details of the study site monitoring process are described in a separate clinical monitoring plan document.

9 STATISTICAL METHODS AND DATA ANALYSIS

Statistical methods will be documented in detail in a statistical analysis plan (SAP) for Part 1, and a separate SAP for each of independent Part 2A and Part 2B, to be approved by the Sponsor prior to unblinding and database lock for the respective parts of the study. Deviations from the approved SAPs will be described and justified in the clinical study report(s).

9.1 Statistical Hypothesis

The primary endpoint is change from Baseline in the SAPS-H+D total score at Week 6. The primary endpoint will be compared between each of the ACP-204 dose groups (30 mg, 60 mg) and the placebo group.

Let Δ be the difference in the mean change from Baseline in the SAPS-H+D total score at Week 6 between the ACP-204 group and the placebo group:

The null hypothesis for the primary endpoint is: $\Delta = 0$ The alternative hypothesis for the primary endpoint is: $\Delta \neq 0$

The key secondary endpoint is CGI-I-ADP score at Week 6; it will be compared between each of the ACP-204 dose groups (30 mg, 60 mg) and the placebo group.

Let Δ be the difference in the mean at Week 6 in the CGI-I-ADP score between the ACP-204 group and the placebo group:

The null hypothesis for the key secondary endpoint is: $\Delta = 0$ The alternative hypothesis for the key secondary endpoint is: $\Delta \neq 0$

9.2 Multiplicity Adjustment

In order to control the overall type I error rate, the multiplicity will be adjusted for multiple comparisons of 30 mg versus placebo and 60 mg versus placebo for the primary endpoint and key secondary endpoint. Details of the multiplicity control procedure will be provided in the SAP.

9.3 Sample Size Determination

Part 1:

In Part 1, approximately 318 subjects will be randomized in a 1:1:1 ratio to ACP-204 60 mg (n=106), ACP-204 30 mg (n=106), or placebo (n=106). After allowance of 5% non-evaluable subjects, at least 100 evaluable subjects will be randomized per treatment group. This will provide at least 80% power to detect a standard effect size 0.4 between either ACP-204 dose (n=100) and placebo (n=100) at an alpha level of 0.05 using a two-sided test.

Part 2A and Part 2B:

In each of Part 2A and Part 2B of the study, approximately 378 subjects will be randomized in a 1:1:1 ratio to ACP-204 60 mg (n=126), ACP-204 30 mg (n=126), or placebo (n=126), to include at least 360 evaluable subjects after allowance of 5% non-evaluable subjects. These 360 subjects, with two active ACP-204 doses should provide at least 85% power to detect a standard effect size 0.4 between either ACP-204 dose (n=120) and placebo (n=120) at an alpha level of 0.05 using a two-sided test.

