9.7 Efficacy Analyses

All efficacy endpoints will be analyzed and summarized by treatment group using the Full Analysis Set of Part 1 and the Full Analysis Sets of independent Part 2A and Part 2B, respectively. The Full Analysis Sets of Part 2A and Part 2B will be analyzed separately from each other and independently from the Full Analysis Set of Part 1.

All efficacy endpoints will be summarized by treatment group using descriptive statistics.

All efficacy statistical tests will be two-sided hypothesis tests performed at an alpha level of 0.05. In addition, all confidence intervals will be two-sided 95% confidence intervals, unless stated otherwise.

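### Section 9.3 states power for either dose at a full 0.05 per comparison although Section 9.2 adjusts for two doses; after adjustment Part 1 misses 80% for at least one dose, and Part 2 depends on the procedure

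*Protocol*

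**What the plan says.** Section 9.3 of the protocol, repeated in the synopsis, gives one power statement for each phase. For Part 1: "This will provide at least 80% power to detect a standard effect size 0.4 between either ACP-204 dose (n=100) and placebo (n=100" per arm). For each of Part 2A and Part 2B, 360 evaluable subjects "should provide at least 85% power to detect a standard effect size 0.4 between either ACP-204 dose (n=120) and placebo (n=120" per arm). Both are stated "at an alpha level of 0.05 using a two-sided test". The numbers randomised, 106 and 126 per arm, include a 5% allowance for non-evaluable subjects.

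Section 9.2, immediately before, says that "the multiplicity will be adjusted for multiple comparisons of 30 mg versus placebo and 60 mg versus placebo", on the primary and the key secondary endpoint, to control the overall type I error. It leaves the procedure to the SAP, which is a normal division of labour.

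The analysis sections return to the unadjusted level. Section 9.7 says: "All efficacy statistical tests will be two-sided hypothesis tests performed at an alpha level of 0.05". Sections 9.7.2 and 9.7.3 also test at two-sided 0.05, and none of the three refers back to Section 9.2.

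**The concern.** Section 9.3 offers its figures as the power for either dose against placebo. They come from a test in which each dose has the whole 0.05 to itself, which Section 9.2 rules out for the two doses jointly. The power statement and the planned test are therefore not about the same thing.

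Section 1.4.1 relies on these sizes to say that each part has enough power to stand on its own. Part 1 is the proof-of-concept and dose-finding read-out. A dose with a true effect of 0.4 that misses significance there should be read against the real chance of a miss. The protocol implies at most 20%. Under the procedures checked below it is about 22% to 31%, unless that dose is tested first in a fixed sequence.

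**Working it through.** **Inputs, all from Section 9.3 unless noted.** Standardised effect d = 0.4; n = 100 per arm (Part 1) and 120 per arm (each of Part 2A and Part 2B); two-sided alpha 0.05; 1:1:1 allocation; two dose comparisons sharing one placebo arm, adjusted (Section 9.2). The 5% allowance checks: 106 × 0.95 = 100.7 and 126 × 0.95 = 119.7.

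**Step 1: reproduce the stated figures.** Normal approximation: power = Φ(d·√(n/2) − z), with z = 1.960 at 0.05.
- n = 100: 0.4 × √50 = 2.828; 2.828 − 1.960 = 0.868; power 80.7%. Exact t: 80.4%.
- n = 120: 0.4 × √60 = 3.098; 3.098 − 1.960 = 1.138; power 87.3%. Exact t: 87.0%.

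Both statements are true at an unadjusted 0.05. Part 1 has no slack: 99 per arm gives 79.97% by the t test. Part 2 has about two points.

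**Step 2: an equal split of alpha.** With z = 2.241 at 0.025:
- n = 100: 2.828 − 2.241 = 0.587; power 72.1%. Exact t: 71.5%.
- n = 120: 3.098 − 2.241 = 0.857; power 80.4%. Exact t: 80.0%.

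**Step 3: other standard procedures.** These were simulated with 1,000,000 replicates, three arms, shared placebo (correlation 0.5) and a pooled SD. Pooling over three arms moves the results a few tenths of a point from Steps 1 and 2. Rejection rules for dose A (B is the other dose):
- Holm: A at 0.025, or B at 0.025 and A at 0.05.
- Hochberg: A at 0.025, or both at 0.05.
- Fixed sequence: first dose at 0.05; second dose only if both pass 0.05.

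Power (%) with both true effects at 0.4:

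| Procedure | Part 1, per dose | Part 1, at least one | Part 2, per dose | Part 2, at least one |
|---|---|---|---|---|
| No adjustment | 80.5 | 91.6 | 87.1 | 95.3 |
| Bonferroni | 71.7 | 85.6 | 80.1 | 91.3 |
| Single-step Dunnett | 72.7 | 86.3 | 81.0 | 91.9 |
| Holm | 77.0 | 85.6 | 84.7 | 91.3 |
| Step-down Dunnett | 77.5 | 86.3 | 85.1 | 91.9 |
| Hochberg | 78.0 | 86.6 | 85.5 | 92.1 |
| Fixed sequence, first dose | 80.5 | 80.5 | 87.1 | 87.1 |
| Fixed sequence, second dose | 69.5 | – | 78.9 | – |

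**Step 4: the other dose is weaker.** If it has effect 0 to 0.2, the dose with effect 0.4 has about 72–73% in Part 1 and 80–81% in Part 2 under Bonferroni, Holm and Hochberg. The step-up and step-down gains largely vanish because they depend on the other dose also succeeding.

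**The case against.** **The arithmetic is right and the alpha is disclosed.** This stands. Section 9.3 states its alpha, effect and sample size, and the figures follow. The fault is an input that does not match the planned test, not a miscalculation.

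**The procedure belongs to the SAP, and a fixed sequence would keep the full 0.05 for the first dose.** This also stands, and it means that no single adjusted figure can be called the power of this design. It does not rescue the Part 1 claim, which is made for either dose: in a fixed sequence the second dose has 69.5%.

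**Either dose could mean at least one dose.** On that reading Part 1 would exceed 80% under every procedure in the table if both doses work. But the statement pairs one dose with placebo, 100 against 100, and 80.4% is the pairwise result. At-least-one power would be a different number and would need both effects assumed.

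**Part 2 was given a floor below its computed value.** This is largely right. With both effects at 0.4, 85% is met under Hochberg and step-down Dunnett and missed by 0.3 points under Holm. The shortfall is clear only under Bonferroni, single-step Dunnett, for the second dose of a fixed sequence, or when the other dose is weak under a non-sequential procedure. That last case is not remote, since Section 3.1 allows Part 2 to confirm a single dose.

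**Two stronger readings are not supported.** A reader might infer from Sections 9.7 to 9.7.3 that both doses are tested at an unadjusted 0.05, with a family-wise error near 9% on the primary endpoint. Section 9.2 expressly covers these comparisons, so that is not the plan; only a cross-reference is missing. A reader might also infer a further loss from dropout before Week 6. The protocol gives no dropout rate or within-subject correlation, and its mixed model uses partial data. Purely as an assumed sensitivity range, an effective fraction of 0.84 to 0.94 would put unadjusted Part 1 power at about 73–78%. That is separate from this point.

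**Conclusion.** Wrong as written. The power in Section 9.3 and the synopsis is per comparison before adjustment but is presented as the power for either dose in a design that adjusts for two.

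In Part 1 the claim of at least 80% for either dose fails, for at least one dose, under every procedure checked; only a dose placed first in a fixed sequence keeps it. In Part 2A and Part 2B, per-dose power runs from about 79% to 87% when both doses work, so whether 85% is reached depends on the procedure and on the other dose.

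The figures assume a true standardised effect of 0.4, the stated evaluable numbers all contributing at Week 6, equal variances, and alpha split or ordered between the doses on the primary endpoint. Error control is not in question, and the result does not show that the trial is too small to be worth running.

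**What to change.** In Section 9.3 and the synopsis, do one of two things:
- name the multiplicity procedure and restate power under it, per dose and for at least one dose, giving the effect assumed for each dose; or
- say that the quoted power is per comparison before adjustment, and set the adjusted value beside it once the procedure is fixed.

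No adjusted range should be inserted before a procedure is named, because the values differ between procedures and, in a fixed sequence, between doses.

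In Sections 9.7, 9.7.2 and 9.7.3, and in the matching synopsis text, replace the per-test 0.05 for the primary and key secondary comparisons with an overall two-sided 0.05 under Section 9.2.

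The cost is wording only, and the stated power becomes less favourable, mainly in Part 1. Enrolment, the endpoint and the analysis model do not change.

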9.4 Descriptive Statistics

Continuous measurement results will be reported using the number of subjects with data values, mean, standard error of the mean, standard deviation, minimum, maximum, and median. For each categorical outcome, the number and percentage of subjects in each category will be reported.

9.5 **Missing Data**

Handling of missing values will be described in detail in the SAP. Sensitivity analyses will be performed to assess the impact of missing data on the robustness of primary analysis results.

9.6 **Analysis Sets**

Part 1 of Study ACP-204-006 will be locked, unblinded, and analyzed while Part 2A and Part 2B are ongoing.

Part 2A or Part 2B will be analyzed independently from each other and independently from the Part 1 analysis.

The Randomized Analysis Sets of Part 1, Part 2A, and Part 2B include all subjects who were randomized in Part 1, Part 2A, or Part 2B, respectively.

The Randomized Analysis Sets will be used for analyses specified in the SAP based on the randomized treatment assignment.

The Safety Analysis Sets of Part 1, Part 2A, and Part 2B include all randomized subjects in Part 1, Part 2A, or Part 2B, respectively, who received at least one dose of study drug (ACP-204 or placebo). Subjects will be analyzed based on the treatment they actually received.

The Safety Analysis Sets will be used for all safety analyses.

The Full Analysis Sets of Part 1, Part 2A, and Part 2B include all randomized subjects in Part 1, Part 2A, or Part 2B, respectively, who received at least one dose of study drug and who have both a baseline value and at least one post-baseline value for SAPS-H+D total score. Subjects will be analyzed based on their planned randomized treatment.

The Full Analysis Sets will be used for the analysis of all efficacy endpoints.

The PK Analysis Set includes all subjects in the Safety Analysis Set who have sufficient PK data to derive at least one PK parameter.

Any other analysis sets, if necessary, will be defined in the SAP.

9.7 Efficacy Analyses

All efficacy endpoints will be analyzed and summarized by treatment group using the Full Analysis Set of Part 1 and the Full Analysis Sets of independent Part 2A and Part 2B, respectively. The Full Analysis Sets of Part 2A and Part 2B will be analyzed separately from each other and independently from the Full Analysis Set of Part 1.

All efficacy endpoints will be summarized by treatment group using descriptive statistics.

All efficacy statistical tests will be two-sided hypothesis tests performed at an alpha level of 0.05. In addition, all confidence intervals will be two-sided 95% confidence intervals, unless stated otherwise.

9.7.1 Estimand

The primary estimand defining the treatment effect of interest in this study uses the hypothetical strategy specified in the ICH E9 (R1) Addendum. The estimand, or target of estimation, following the hypothetical strategy is the pharmacological effect seen, had no study treatment discontinuation occurred. This hypothetical estimand is justifiable in this case, since the focus is on the pharmacological effect of the drug additional to non-specific effects. Subjects who discontinue from a study treatment either could have lost their treatment effect, had the subjects not taken any other symptomatic medication after the discontinuation of study treatment, or could have had their treatment effect masked, had the subjects taken other symptomatic medication after the discontinuation of study treatment. This means that any observations taken after subjects stop study medication will most likely not contribute relevant information about the pharmacological effect of the study drug.

By this strategy, the last collected efficacy assessment after premature treatment discontinuation will be done only at the ET visit. Every effort will be made to complete the ET evaluations prior to administering any additional medications for the treatment of ADP or other prohibited medications. In the case of lost to follow-up events or death, no ET evaluations are expected, and only scheduled assessments performed before such an event are expected.

In this hypothetical strategy, the event of premature discontinuation of study medication is considered missing at random (MAR), and the primary endpoint of the study could be considered as a combination of the responses of on-treatment completers at Week 6 and the imputation of the endpoint to Week 6 following the trend in each treatment group using the mixed-effect model repeated measures (MMRM) method for subjects who discontinuation study drug during the study. All data collected during the study treatment period will be used for statistical analysis. Under the MAR assumption, MMRM provides an unbiased estimate of treatment effect for the treatment period.

The primary estimand for this study is defined by the following components:

- a. **Target population**: Full Analysis Set
- b. Variable (primary endpoint): Mean change from Baseline to Week 6 in the SAPS-H+D total score
- c. **Treatment condition**: ACP-204 60 mg, ACP-204 30 mg, or placebo
- d. **Intercurrent events**: Premature treatment discontinuation; the hypothetical estimand is to evaluate the pharmacological effect as if no treatment discontinuations had occurred.
- e. Measure of intervention effect: Difference in endpoint means between ACP-204 and placebo arms as if had no subject discontinued the treatment

9.7.2 **Primary Estimator**

The primary endpoint is the change from Baseline in the SAPS-H+D total score at Week 6. The primary analysis will evaluate treatment effect of ACP-204 60 mg and ACP-204 30 mg compared to placebo based on the Full Analysis Set using the MMRM. The model will include effects for treatment groups, visit, treatment-by-visit interaction, baseline SAPS-H+D total scoreby-visit interaction, and randomization stratification factors (site, institution status [yes or no]). An unstructured covariance matrix will be used to model the within-subject errors, and the Kenward-Roger approximation will be used to adjust the denominator degrees of freedom. The treatment effect will be estimated by the difference in least squares means of SAPS-H+D total score at Week 6 and will be tested at an alpha level of 0.05 (two-sided) using the Full Analysis Set of Part 1 and Full Analysis Sets of Part 2A and Part 2B, respectively. The difference in least squares means, corresponding 95% confidence interval, and p-value will be reported.

9.7.3 **Key Secondary Endpoints Analyses**

The key secondary efficacy endpoint, CGI-I-ADP score at Week 6, will be analyzed in a similar fashion as the primary endpoint. The model will include effects for treatment groups, visit, treatment-by-visit interaction, randomization stratification factors (site, institution status [yes or no]), baseline CGI-S-ADP score, and baseline CGI-S-ADP score-by-visit interaction. The

treatment effect will be estimated by the difference in least squares means of CGI-I-ADP score at Week 6 and will be tested at an alpha level of 0.05 (two-sided) using the Full Analysis Set of Part 1 and Full Analysis Sets of Part 2A and Part 2B, respectively. The difference in least squares means, corresponding 95% confidence interval, and p-value will be reported.

9.7.4 Other Secondary and Exploratory Endpoints Analyses

The other secondary and exploratory efficacy endpoints are listed in Section 2.2.2.1 and Section 2.3.1, respectively.

For analysis of continuous efficacy endpoints, the analysis method will be the same as that used for the primary variables, except for QOL-AD score and SDI score. The QOL-AD score and SDI score will be analyzed using analysis of covariance. For analysis of categorical variables in other secondary efficacy endpoints (e.g., proportional analysis), the Cochran Mantel Haenszel approach stratified by the randomization strata will be used. All other (i.e., not key) secondary and exploratory efficacy analyses will be performed using the Full Analysis Set of Part 1 and Full Analysis Sets of Part 2A and Part 2B, respectively.

9.8 Safety Analyses

All safety analyses will be performed using the Safety Analysis Set of Part 1 and Safety Analysis Sets of Part 2A and Part 2B, respectively. Safety data collected on or after the first dose of study drug administration up to 30 days after the last dose of study drug, unless specified otherwise, will be summarized by treatment group using descriptive statistics. No formal statistical testing will be performed for any of the safety endpoints.

The safety endpoints are (Section 2.4.1):

- TEAEs
- 12-lead ECGs
- Vital signs, including orthostasis assessment
- Weight and BMI
- Physical examination results
- Clinical laboratory tests
- GCAS score
- C-SSRS
- UKU Sleepiness/Sedation and Orthostatic Dizziness scores
- MMSE score
- DSST score

ESRS-A scores

9.8.1 **Adverse Events**

All AEs will be classified into standard terminology using the Medical Dictionary for Regulatory Activities coding dictionary.

Treatment-emergent adverse events are:

• Any AEs with an onset date of on or after the study drug start date and no later than 30 days after permanent discontinuation of study drug

All AEs will be listed, and TEAEs will be summarized by system organ class and preferred term. Treatment-emergent adverse events, TEAEs leading to discontinuation, TEAEs related to study drug, TEAEs by maximum severity, fatal TEAEs, serious TEAEs, and serious TEAEs related to study drug will all be summarized by treatment group. Adverse events of special interest (AESIs) will be summarized by treatment group as well. Investigator-reported AESIs will populate the primary safety table, and neurologist-evaluated events will be summarized separately in supplemental safety tables in the final study report.

Deaths of subjects who discontinue prematurely from the study that occur between 30 days after the last dose of study drug and 30 days after the subject's intended day of last dose of study drug will be summarized separately.

9.8.2 ECGs, Vital Signs, Weight and BMI, Physical Examination Results, and Clinical **Laboratory Tests**

Descriptive statistics for ECG, vital signs and weight, and clinical laboratory parameters, including change from Baseline, will be tabulated by visit and treatment group. The results of the physical examinations at each visit will be tabulated by treatment group. Categorical analyses will be conducted on the incidence of subjects with prolonged QTc intervals and changes in QTc intervals in accordance with ICH guidelines and based on the US Food and Drug Administration (FDA) E14 Guidance Document.

The number and percentage of subjects with potentially clinically important post-baseline values will be summarized for selected parameters. The criteria for potentially clinically important values will be specified in the SAP.

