Safety Follow-up Period (30 Days) for Subjects Not Rolling Over into OLE

Subjects who successfully complete the 6-week Double-blind Treatment Period may be eligible to enroll in an OLE study (ACP-204-008). For subjects who discontinue prematurely from the study, two Safety Follow-up visits (telephone calls to the subject and study partner/caregiver) should be conducted, at 7 ± 3 days and 30 ± 4 days after the last dose of study drug, provided the subject or the subject's legally acceptable representative (LAR) has not withdrawn consent from further data collection.

Mortality Follow-up for ET Subjects

In addition to the safety follow-up telephone calls during the Safety Follow-up Period, for subjects who discontinue prematurely from the study and have not withdrawn consent (or had consent withdrawn by LAR) from further data collection, a telephone call to the subject and/or study partner/caregiver to confirm that the subject is still living will be conducted 30 (+4) days after the subject's intended day of last dose of study drug (i.e., the day that their last dose of study drug would have been taken had they not

Final Version: 2.0

	discontinued prematurely). If a subject has died in this follow-up period, every effort will be made where possible to collect the cause of death. End of Study For subjects enrolling into Study ACP-204-008, a subject is considered to have completed this study if he/she has completed the EOT visit for Part 1 or Part 2A or Part 2B of this study and has not had an ET from the study. For subjects not enrolling into Study ACP-204-008, a subject is considered to have completed this study if he/she has completed all visits, including the Safety Follow-up visit at 30 (+4) days after the last dose of study drug, for Part 1 or Part 2A or Part 2B of the study.
	Data and Safety Monitoring Board
	An independent data and safety monitoring board (DSMB) will review safety information on a regular basis throughout the study.

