Visit day/Week	•	/ -49 ater	Week 0	Week 1	Week 2	Week 4	Week 6	Visit 6 +7 days	Visit 6 +30 days	Week 6 +30 days
Visit number	1a	1b	Baseline 2	3	4	5	(EOT/ET) 6	7	8	9
Visit window (days)				±3	±3	±3	±3	±3	+4	+4
Type of visit	Clinic	Clinic	Clinic	Clinic	Clinic	Clinic	Clinic	Phone call	Phone call	Phone call
Informed consent/assent	Xs						Xp			
Inclusion/exclusion criteria		X	X							
Clinical Validation Inventory for Study Admission		X								
Medical history and demographics		X								
Psychiatric, dementia, and neurological history		X								
Physical and neurological examination		X	X				X			
Brief Psychosocial Therapy		X^q								
Vital signs (including orthostatic changes) ^b and weight		X	X	X	X	X	X			
Assessment of peripheral edema		X	X	X	X	X	X			
Height		X								
12-lead ECG ^c		X	X	X	X	X	X			
Clinical laboratory tests ^d	X		X ⁿ		X		X			
Biomarkers for Alzheimer's disease for eligibility blood sampling	X									
Urine toxicology screen ^e	X		X				X			
COVID-19 test ^f	X									
MMSE		X	X	X	X	X	X			

Table continued on next page.

Table S-1 Schedule of Events and Assessments for ACP-204-006 in Part 1, Part 2A, and Part 2B (Continued)

Period	Screening			Double-bl	ind Treatm	Safety Follow-up ^a		Mortality Follow-up ^o		
Visit day/Week		-49 ater	Week 0	Week 1	Week 2	Week 4	Week 6	Visit 6 +7 days	Visit 6 +30 days	Week 6 +30 days
Visit number	1a	1b	Baseline 2	3	4	5	(EOT/ET) 6	7	8	9
Visit window (days)				±3	±3	±3	±3	±3	+4	+4
Type of visit	Clinic	Clinic	Clinic	Clinic	Clinic	Clinic	Clinic	Phone call	Phone call	Phone call
DSST		X	X	X	X	X	X			
SAPS-H+D		X	X	X	X	X	X			
NPI or NPI-NHg		X	X		X	X	X			
NPI-C hallucinations and delusions domains ^h		X	X		X	X	X			
CGI-S-ADP		X	X	X	X	X	X			
CGI-I-ADP				X	X	X	X			
GCAS ⁱ		X	X	X	X	X	X	X	X	
C-SSRS ⁱ		X	X	X	X	X	X	X	X	
ESRS-A			X	X	X	X	X			
QOL-AD			X				X			
EQ-5D-5L ^j							X			
UKU Sleepiness/Sedation and Orthostatic Dizziness		X	X	X	X	X	X			
SDI			X				X			
Brain MRI or CT ^k		X								
Assessment of concomitant (or post-treatment) medications/procedures	X	X	X	X	X	X	X	X¹	X ^l	
Assessment of adverse events	X	X	X	X	X	X	X	X	X	
Randomization			X							
Dispense study drug			X		X	X				

Table continued on next page.

Table S-1 Schedule of Events and Assessments for ACP-204-006 in Part 1, Part 2A, and Part 2B (Continued)

Period	Screening		Double-blind Treatment Period					Safety Follow-up ^a		Mortality Follow-up ^o	

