- This Safety Follow-up Period includes two telephone calls (each to the subject and study partner/caregiver) for subjects who discontinue prematurely from the study, or who complete the treatment period of the study and do not rollover into the open-label extension study. These telephone calls will occur at 7 (±3) days and 30 (+4) days after the last dose of study drug, provided the subject or LAR has not withdrawn consent from further data collection.
- Vital signs will include body temperature, resting respiration rate, and orthostatic blood pressure (systolic and diastolic) and pulse rate. Blood pressure and pulse rate will be measured after the subject rests for 5 minutes in the supine position. The subject will then be asked to stand, and blood pressure and pulse

rate will be taken after standing for approximately 1 minute and then again after the subject has been standing for approximately 3 minutes (no later than 5 minutes). Subjects unable to stand may be assessed while sitting upright. The same position and arm should be used each time vital signs are measured for a given subject. Orthostatic hypotension is defined as a decrease in systolic blood pressure \geq 20 mmHg or diastolic blood pressure \geq 10 mmHg after transitioning from the supine position (after resting for 5 minutes) to standing after 1 or 3 minutes. If orthostatic hypotension is present, the Investigator should determine if the subject has associated symptoms such as postural dizziness or pre-syncope, as measured by UKU orthostatic dizziness severity greater than zero, or history of falls associated with orthostatic hypotension. If a subject with orthostatic hypotension at Screening or Baseline has associated symptoms, this will be exclusionary.

- The 12-lead ECG will be completed in triplicate at Screening. A single ECG will be completed at all other visits. The ECG should be completed before or at least 30 minutes after any blood sampling.
- Except for when required for eligibility, if collection of a urine sample for clinical laboratory tests (urinalysis) proves impractical or impossible, failure to collect a urine sample should be recorded in the subject's eCRF and will not be considered a protocol deviation.

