3.1.3 Safety Follow-up Period (30 Days) for Subjects Not Rolling Over into OLE

Subjects who successfully complete the 6-week Double-blind Treatment Period may be eligible to enroll in an OLE study (ACP-204-008). For subjects who discontinue prematurely from the study, two Safety Follow-up visits (telephone calls to the subject and study partner/caregiver) should be conducted, at 7 (\pm 3) days and 30 (\pm 4) days after the last dose of study drug, provided the subject or the subject's legally acceptable representative (LAR) has not withdrawn consent from further data collection.

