6.7 Safety Follow-up

A 30-day Safety Follow-up Period, incorporating two telephone calls to the subject and study partner/caregiver, at 7 (±3) days and 30 (+4) days after the last dose of study drug, is to be completed for subjects who complete the Double-blind Treatment Period of the study and decide not to continue into the OLE study or are not eligible for the OLE study, as well as those who discontinue prematurely from the study. Subjects should have the following completed during both telephone calls per Table S–1:

- Assessment of concomitant medications/treatments
- Assessment of AEs
- GCAS
- C-SSRS

The follow-up telephone call at $7 (\pm 3)$ days after the last dose of study drug should be utilized to evaluate any new adverse events after discontinuation of study drug and any ongoing adverse events.

See Section 4.5.1 for additional information, including limitations in case of withdrawal of consent.

Final Version: 2.0

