9.8.3 GCAS, C-SSRS, UKU Sleepiness/Sedation and Orthostatic Dizziness, MMSE, **DSST**, and ESRS-A

UKU Sleepiness/Sedation and Orthostatic Dizziness, MMSE, DSST, and ESRS-A scores and changes from Baseline will be summarized by treatment group and visit and will be analyzed using an MMRM model similar to the primary analysis. For the GCAS, the number and

Final Version: 2.0

Study: ACP-204-006 Final Version: 2.0 Clinical Study Protocol Amendment 3 Date: 15 October 2024

percentage of subjects with a score of 3 or 4 during the study will be tabulated. For the C-SSRS, the summary descriptive statistics will be tabulated.

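### The 30-day cut for safety summaries falls on the first permitted day of the final follow-up call, so on-time C-SSRS ratings from days 31 to 34 are left out by default

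*Protocol*

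**What the plan says.** **Analysis period.** Section 9.8 lists the GCAS and C-SSRS among the safety endpoints and sets one default period for all of them: "Safety data collected on or after the first dose of study drug administration up to 30 days after the last dose of study drug". The same sentence carries an exception clause, since it covers data "up to 30 days after the last dose of study drug, unless specified otherwise, will be summarized by treatment group using descriptive statistics".

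**Timing of the last call.** The Safety Follow-up footnote to Table S-1 reads: "These telephone calls will occur at 7 (±3) days and 30 (+4) days after the last dose of study drug". Section 6.7 gives the same timing and lists the GCAS and C-SSRS among the items to be completed at both calls. For early discontinuers, however, the synopsis places the calls "at 7 ± 3 days and 30 ± 4 days after the last dose of study drug", and Section 3.1.3 repeats ± 4 for the second call.

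**Who has the call.** Early discontinuers, and completers who do not enter the extension study.

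**Scale-specific rules.** Section 9.8.3 says that for the GCAS the number and "percentage of subjects with a score of 3 or 4 during the study will be tabulated". For the C-SSRS it promises descriptive statistics and names no period.

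**What the ratings cover.** Section 6.3.7 has the GCAS rate suicidality since the previous visit. Section 6.3.8 uses the Since Last Visit form of the C-SSRS at every visit after Screening.

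**The concern.** A visit window with only a plus side allows the call to be late but not early. If the analysis period ends on the first day of that window, nearly all of the permitted slack lies outside the analysis. A site can follow the schedule exactly and still produce a rating that the summary rule excludes.

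Adverse events do not have this problem. Section 9.8.1 defines TEAEs by onset date, so an event that began by day 30 and was first reported on day 33 still counts. The Section 9.8 default turns instead on when data were collected, and for a rating scale that is the date of the call. A C-SSRS rating on day 32 is therefore excluded even if the ideation or behaviour it records occurred on day 20.

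At stake is the last suicidality rating after study drug is stopped, in the subjects who left early or did not roll over. Positive ratings are likely to be few, so a single omission could be visible in a by-arm table.

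**Working it through.** The protocol states no figure on this point, so there is none to reproduce. The check is a count of days and a comparison of sections.

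**1. Permitted call days after the cut** (cut: day 30 after the last dose, Section 9.8)

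| Wording of the window | Where | Permitted days | Days after 30 | Share of days |
|---|---|---|---|---|
| 30 (+4) | Table S-1 and its footnote, Section 6.7 | 30 to 34 (5 days) | 31 to 34 (4 days) | 4/5 = 80% |
| 30 ± 4 | Synopsis and Section 3.1.3, early discontinuers | 26 to 34 (9 days) | 31 to 34 (4 days) | 4/9 = 44% |

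**2. From days to ratings.** The table counts days, not ratings. Under +4, the share of ratings outside the cut is 1 minus the share of calls made on day 30 exactly. The protocol does not give that share. As an assumed range:

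- 20% of calls on day 30: 1 − 0.20 = 80% outside
- 50% of calls on day 30: 1 − 0.50 = 50% outside
- 80% of calls on day 30: 1 − 0.80 = 20% outside

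**3. How much of the look-back lies inside the 30 days.** Take the previous visit to be the first follow-up call, at 7 (±3) days, so on day 4 to 10. For a final call on day *d*, the share of the look-back inside the period is (30 − first call) / (*d* − first call).

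- First call day 4, final call day 31: 26/27 = 96%
- First call day 7, final call day 34: 23/27 = 85%
- First call day 10, final call day 34: 20/24 = 83%

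So between 83% and 96% of the time covered by an excluded rating lies within the 30 days that the analysis is meant to describe.

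**4. Is a different period given for either scale?**

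- *C-SSRS:* no. Section 9.8.3 is silent, so the default applies. Section 9.8.1 does make separate provision for one kind of data after day 30, deaths among early discontinuers. Nothing similar exists for the C-SSRS.
- *GCAS:* probably yes. Section 9.8.3 refers to the study as a whole. Section 3.1.5 counts a subject not entering the extension as having completed the study only after all visits, including the 30 (+4)-day follow-up visit. Read together, these bring Visit 8 into the GCAS table, but no sentence says so.

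**5. After the change.** If both scales are summarised through the end of the Visit 8 window (day 34 under either wording), 0 of 5 or 0 of 9 permitted days fall outside.

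**The case against.** The strongest reply is that Section 9.8 sets a default and not an absolute limit. It allows other periods to be specified, and Section 9 leaves detailed methods to the SAPs, which are not shown. Mapping visits to analysis windows is ordinary SAP content. This stands in part: a SAP could settle the matter. But the protocol does more than leave a gap. It fixes a cut that does not fit its own schedule, and each SAP that follows it literally would carry the mismatch into its part of the study.

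Four stronger readings are tempting, and the documents do not support them.

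- *That late GCAS ratings are lost as well.* Sections 9.8.3 and 3.1.5 together point the other way. The wording is implicit, but exclusion is not established.
- *That most final ratings, or 80% of them, are excluded.* That needs calls spread evenly over days 30 to 34. It also ignores the ± 4 wording, under which fewer than half of the permitted days are affected.
- *That Table S-1 ties the call to Visit 6, which would push it past day 30 for any early terminator whose termination visit followed the last dose.* The column header "Visit 6 +30 days" can be read that way, but the footnote to the same column, and Section 6.7, tie the call to the last dose.
- *That suicidality first learned of on days 31 to 34 disappears from safety reporting.* If it is recorded as an adverse event with onset by day 30, it enters the TEAE tables. Investigators must also assess any sign of suicidality on either scale, whatever the later summary includes.

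**Conclusion.** The point holds in a limited form. Read as written, the default in Section 9.8 excludes C-SSRS ratings made on schedule on days 31 to 34, and nothing else in the protocol restores them. That is 4 of 5 permitted days under +4, or 4 of 9 under ± 4. The protocol gives neither the distribution of call dates nor an expected rollover rate, so no count of subjects or ratings can be stated. Only subjects who do not enter the extension are affected.

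The loss is confined to a descriptive by-arm summary. Data collection, the primary analysis, the type I error rate and every formal test are untouched. It is still worth correcting, because the excluded ratings mainly describe time inside the intended 30 days. Separately, the +4 and ± 4 versions of the same call contradict each other and must be reconciled.

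**What to change.** - In Section 9.8 or 9.8.3, and in the SAP for each part, state that the C-SSRS and GCAS are summarised through Visit 8 including its permitted window. This also makes the GCAS reading explicit.
- Keep the 30-day onset rule for TEAEs unchanged.
- Reconcile the +4 wording (Table S-1, Section 6.7) with the ± 4 wording (synopsis, Section 3.1.3) for the final call.

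The cost is one sentence in the protocol, the matching line in each SAP, and an editorial correction of the window. No new data, visits or subjects are needed. The rule should be settled before each part is unblinded, since choosing a safety cut afterwards would be a post hoc decision.
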